## 2.2 Exploratory objectives

5. To explore the association between maternal CMV shedding in vaginal fluid and breast milk and the risk of congenital CMV infection assessed by quantitative CMV PCR.
6. Determine the incidence of postnatal CMV acquisition, in infants not CMV infected at birth, and explore possible risk factors, including maternal HIV status and the magnitude of maternal CMV shedding in vaginal fluid and breast milk.
7. Explore differences in immune responses to the primary and booster series of vaccinations (DTaP-Hib/HepB, PCV rotavirus and measles vaccines) between congenital CMV cases, postnatally acquired CMV cases and non-CMV infected controls at 6, 12 and 13 months of age.

## 3 Research Methods

### 3.1 Study Site

This study will be conducted at Chris Hani Baragwanath Academic Hospital (CHBAH) in Soweto, a secondary-tertiary level facility serving a population of 1.2 million. The annual birth cohort in Soweto is approximately 28000, with 75% occurring at CHBAH and the rest at midwife operated units or a nearby district level hospital.

### 3.2 Overview of study

This will be an epidemiologic cross-sectional study, with a prospective cohort component (refer to [Appendix 2](#) for study schema). Objectives 1, 2 and 5 will be nested within a larger cohort study enrolling mother-infant dyads at birth or antenatally to investigate a sero-correlate of protection against invasive Group B Streptococcal disease in newborns ( protocol number V98\_28OBTP, HREC no. 140203, [Appendix 4](#)). In V98\_28OBTP, research staff at labour/delivery wards identifies women enrolled antenatally or consents potentially interested women in labour for participation. Maternal and infant demographic and clinical data, maternal blood, vaginal swab and infant cord blood are collected for laboratory testing. Monitoring for subsequent hospitalization of the infant at CHBAH in the first year of life is undertaken daily in all general paediatric and neonatal wards in an established surveillance known as Babies of Soweto Study (BoSS). As of November 2015, 20 000 mother-newborn dyads are enrolled, and is anticipated to continue until October 2016.

Objective 4 will be nested within a prospective study of cause of death in under-5 children by Minimally Invasive Tissue Sampling (MITS) currently underway at CHBAH ([Appendix 13](#), HREC no. 150215). Stillborn babies are also enrolled into this study.

A summary of objectives, methods and data analysis for this PhD is given in [Appendix 3](#).

### 3.3 Objective 1, 2 and 5 (exploratory) methods

**Study design:** Cross-sectional study design with consecutive sampling

**Study participants:** Mothers meeting the inclusion criteria in table 1 and their newborns.

**Table 1: Maternal inclusion and exclusion criteria**

Inclusion criteria	Exclusion criteria

- Enrolled in V98_28OB

- Age <math>\geq 18</math> years

- Residing in Soweto and would be available for study follow-up

- Consents to enrol self and baby in study

- Baby born alive

	

- <math><18</math> years age

- Visiting Soweto

- Declines consent

Enrolment will be performed by study staff stationed in labour and delivery around-the-clock.

The informed consent form (ICF) used in V98\_28OBTP ([Appendix 4](#)) also allows collection of data and samples from mothers and newborn to test for CMV.

[figure not shown]
**Data collection:** Data will be collected by maternal interview and examination of hospital notes of the mother and newborn, recorded onto the V98\_28OBTP CRF ([Appendix 5](#)) and BoSS CRF ([Appendix 6](#)) if symptomatic. Table 2 describes the maternal and newborn data of interest and figure 1 illustrates the data collection process.

**Table 2: Maternal and newborn data of interest**

Maternal data	Newborn data
Demographic: age, race, and contact details	Demographic: date of birth, gender, race
Clinical data: antenatal care details, past obstetric history, parity, gestation at delivery, delivery details, co-morbidities, HIV status and CD4 count, ART use	Clinical: gestational age at birth, birthweight, head circumference, APGAR scores, HIV exposure, symptoms at birth, discharge or admission details

Newborn saliva samples will be collected by placing an Orocot swab in the mouth for at least 1 minute. All symptomatic neonates for congenital CMV infection ([Appendix 11](#)) will also be screened for other congenital infections which include syphilis, toxoplasmosis, rubella and herpes as is the standard of care at CHBAH.

**Figure 1: Data collection process for Objectives 1, 2 and 5**

All children with any clinical finding are referred to the neonatology department at CHBAH for clinical management as per standard of care. If a newborn PCR indicates CMV infection, the mother will be contacted telephonically to return to the site within two weeks of birth. At this visit the implications of the positive CMV result will be explained and additional consent for the continued follow up of the child (refer to [Appendix 7](#) for ICF and [Appendix 8](#) for schedule of study visits). Should consent be confirmed, a second saliva swab and a urine sample will be collected for PCR to confirm CMV infection. Babies that test CMV negative on both the second saliva swab and urine will not be enrolled as a case as the saliva positivity may be a result of CMV infected breast milk contamination. However, they will be referred for hearing screening as standard of care. Cases testing positive on both saliva and urine or urine alone will continue as cases for objective 3.

Mothers of CMV cases will have a vaginal swab and breast milk collected for quantitative PCR by a research nurse or the investigator. A subset of mothers that tested seropositive for CMV but gave birth to CMV uninfected neonates will also be recalled as controls for the case mothers in a

1:1 ratio, matched by HIV infection, for vaginal fluid and breast milk collection within 2 weeks of delivery.

**Sample size:** Objective 1: Assuming the estimated CMV prevalence is 86% in pregnant women 200 mothers will be needed to estimate the true value with a desired precision of 5% and confidence interval of 95%.

Objective 2: Prevalence of congenital CMV in HIV exposed neonates is 2.9% and in unexposed neonates is 1.0%. Thus, a total sample of 1662 neonates with 831 HIV exposed and 831 unexposed (1:1 ratio) for 80% power, are required to detect a 2.9 fold difference in CMV prevalence between the 2 groups. This will be increased to 2160 neonates, to accommodate objective 3, to determine clinical sequelae in CMV infected infants ([section 3.3.1, Sample size](#)). After adjusting for 10% being non-evaluable, 1077 HIV exposed (providing 31 CMV infected) and 1077 HIV unexposed infants (providing ~11 CMV cases) are required. Ranges of sample size estimates for varying CMV prevalences by HIV exposure are given in [Appendix 9](#).

Objective 5: The number of case mothers tested will be determined by the total number of CMV infected neonates that are identified during screening estimated at 42. HIV infection and age matched control mothers will be allocated in a 1: 1 ratio giving a total sample size of 84.

**Laboratory testing:** Maternal blood and vaginal swabs, newborn saliva and urine collected will be stored at -70 °C until processed for CMV serology (IgG and IgM in blood) and DNA by PCR assays (vaginal fluid, saliva, urine) at the RMPRU Laboratory or other collaborating laboratory in South Africa. The turnover time for PCR testing is expected to be within 5 working days of sample collection. Refer to Appendix 10 for laboratory methods of sample processing.

**Data Analysis:** Table 3 describes the planned data analyses, per objective. All analyses will be done on STATA/IC version 13 for Windows, Texas, USA, in consultation with a biostatistician.

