### 3.4 Objective 3, 6 (exploratory) and 7 (exploratory) Methods

[figure not shown]
***Study design:*** Prospective longitudinal cohort study of CMV infected and uninfected neonates

***Study participants:*** The cohort will consist of newborn infants identified as laboratory confirmed CMV infected from objective 2 forming the cases and a subset of neonates identified as CMV uninfected at birth chosen as controls. Each case will be matched to 2 controls by age, gestational age at birth ( $\pm 2$  weeks) and HIV exposure. Within 2 weeks of age, cases and controls will be recalled to the site to consent for follow up and initiation of investigations as illustrated in figure 2.

***Data collection:*** Postnatal CMV acquisition: A saliva and urine sample from each control infant will be collected at the 2 weeks visit. At subsequent follow up visits, infant saliva and urine will be collected from those that tested CMV negative at the preceding visit.

Incidence of neurological sequelae: neurological sequelae is one or more of: unilateral or bilateral SNHL, developmental deficit, unilateral or bilateral ocular abnormality, abnormal cerebral imaging, microcephaly, or seizures not related to an acute systemic infection or CNS insult (refer to [Appendix 11](#) for case definition of each sequela).

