Antibody to diphtheria toxoid, tetanus-toxoid, pertussis toxoid, filamentous hemagglutinin (FHA) and hepatitis B surface antigen (HBsAg) will be measured by an in-house Luminex multiplex immunoassay. Immune responses to the primary series of PCV will be measured by a standardized enzyme immunoassay (EIA) to test for vaccine serotype-specific capsular immunoglobulin (Ig) G antibody concentrations and opsonophagocytic assay. Titres of rotavirus-specific IgA will be determined in enzyme-linked immunosorbent assays. Refer to appendix 10 for the serological correlates of protection .

**Sample size:** The anticipated prevalence of neurological sequelae in CMV uninfected controls with uneventful foetal or perinatal periods is estimated at 1%. Prevalence of neurological sequelae in CMV infected infants is expected to be higher at approximately 17%. For 80% power, the difference that could feasibly be detected, is 17-fold i.e. 1% vs 17%. Allowing for a loss to follow up of 10%, 42 CMV infected infants and 84 controls (n=126) with an allocation ratio of 1:2 are required ([Appendix 9](#)).

**Data Analysis:** Table 3 describes the data analysis plan to determine the incidence and risk factors for neurological sequelae in congenital CMV infected infants

Table 3: Data analysis plan

Objective 3  Incidence calculation of one or more neurological sequelae for cases and controls at 2 weeks, 2 months, 6 months and 12 months of age dependent on investigations done at each visit  Comparison of proportions with permanent sequelae (hearing impairment and developmental deficit) at each visit between cases and controls using a Z test to compare ratios, including 95% confidence intervals.  Adjust for potential confounders (IUGR, symptoms at birth, gender and co-morbidities) by multiple logistic regression analysis to establish factors contributing to neurological sequelae.
Objective 6  Incidence of postnatal acquisition of CMV in newborns will be calculated at 2 months, 6 months and 1 year of chronological age. Incidence of neurological sequelae in postnatally infected infants will be calculated
Objective 7

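### Objective 6: milk and recall swabs are planned for about 42 control mothers with no stated link to the 84 control infants, so at most half of those infants can have a maternal shedding value from these samples

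*Combined protocol and SAP*

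**What the plan says.** Section 2.2 sets Objective 6 as exploratory. Its first part is to "Determine the incidence of postnatal CMV acquisition, in infants not CMV infected at birth". Its second part is to "explore possible risk factors, including maternal HIV status and the magnitude of maternal CMV shedding in vaginal fluid and breast milk".

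The infants followed for postnatal infection are the cohort controls. Section 3.4 (Data collection) states: "A saliva and urine sample from each control infant will be collected at the 2 weeks visit". Section 3.4 (Study participants) selects them as follows: "Each case will be matched to 2 controls by age, gestational age at birth" (within 2 weeks) and HIV exposure. Maternal serostatus is not a criterion. Section 3.4 (Sample size) gives the number: "42 CMV infected infants and 84 controls (n=126) with an allocation ratio of 1:2 are required".

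Maternal milk and vaginal fluid for Objective 5 are described in Section 3.3, in the text after Figure 1. Case mothers are sampled, and so is "A subset of mothers that tested seropositive for CMV but gave birth to CMV uninfected neonates", recruited in a "1:1 ratio, matched by HIV infection, for vaginal fluid and breast milk collection within 2 weeks of delivery". The Objective 5 sample-size paragraph in the same section adds age to the matching and gives 84 mothers in total.

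Three other places matter. Section 3.2 says the parent study takes a vaginal swab from its mothers. The paragraph after Table 1 says the parent consent covers CMV testing of samples. Section 3.3 (Laboratory testing) stores maternal vaginal swabs for CMV PCR; breast milk is not in that list. The Objective 6 row of the analysis table in Section 3.4 lists incidence only, with no shedding analysis.

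**The concern.** To relate a mother's shedding to her infant's postnatal infection, both must be measured in the same dyad. The infants at risk are the 84 controls. Case mothers cannot contribute, because their infants are already infected at birth. That leaves the control mothers sampled for Objective 5, who are fewer, are chosen by a different rule, and are not said to be the mothers of the cohort's control infants.

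The gap is easy to miss because the number 84 appears in both objectives but counts different people. In Objective 5 it is 42 case mothers plus 42 control mothers. In Objectives 3 and 6 it is 84 control infants.

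Milk matters most here. Section 1.2 itself describes postnatal acquisition through breast milk, and the planned milk sample is taken within two weeks of delivery. A sample not taken in that window cannot be obtained later.

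**Working it through.** **Inputs**
- Expected cases: 1077 HIV-exposed infants at 2.9% and 1077 unexposed at 1.0% (Section 3.3, Sample size, Objective 2).
- Control infants per case: 2 (Section 3.4).
- Control mothers per case mother: 1 (Section 3.3).
- Maternal seropositivity: 86% (Section 3.3, Sample size, Objective 1).
- Neonates screened: 2160 (Section 3.3, Sample size, Objective 2).

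**1. Reproducing the plan's counts**
- Cases: 1077 × 0.029 + 1077 × 0.010 = 31.2 + 10.8 = 42.0.
- Control infants: 42 × 2 = 84; cohort 42 + 84 = 126.
- Objective 5 mothers: 42 × (1 + 1) = 84, of whom 42 are controls.

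All agree with the plan.

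**2. The two selection rules**
- Control infants: two per case; age, gestational age, HIV exposure; any maternal serostatus.
- Control mothers: one per case mother; seropositive only; HIV infection in one paragraph, HIV infection and age in another; gestational age not mentioned.

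Both groups are recalled within two weeks of birth, but neither rule refers to the other.

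**3. Coverage for milk and recall swabs**

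With k control mothers who are also mothers of control infants, coverage is k/84.
- Full overlap: 42/84 = 50%, so 50% missing.
- Half overlap: 21/84 = 25%, so 75% missing.
- No overlap: 0/84, so 100% missing.

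**4. Restricted to seropositive mothers**

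Expected number among the control infants: 0.86 × 84 = 72.2. Best-case coverage: 42/72.2 = 58%.

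**5. How low overlap could fall under the stated rules**

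Uninfected infants: 2160 − 42 = 2118. If both groups were drawn independently at random, the expected overlap is 42 × 84/2118 = 1.7 dyads. This ignores matching and the two-week recall window, so it shows only what the text permits. It does not predict what staff would do.

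**6. Whether one control infant per case could supply the control mother**

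If serostatus is independent between a case's two controls, the chance that at least one mother is seropositive is 1 − 0.14² = 0.98. That is 42 × 0.98 = 41.2 of 42 cases, before any matching on maternal age.

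**7. What halving the dyads does (illustration only)**

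The documents give no shedding or infection rates for this analysis. Assume half of mothers shed and a two-sided 5% comparison of two proportions. Power with 84 and with 42 dyads is:
- Infection 60% v 30%: 0.80 and 0.50.
- Infection 50% v 20%: 0.83 and 0.53.
- Infection 40% v 20%: 0.52 and 0.29.

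**The case against.** Several points on the other side stand.

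- **Vaginal exposure is not limited to 42.** A reader might infer that all vaginal swabs come from the recalled subset. The documents do not support that. Enrolment in the parent study is an inclusion criterion, that study takes a vaginal swab, and its consent allows CMV testing. Vaginal exposure could be available for all 84 control infants. What is missing is a statement that these swabs will be quantified for those mothers.
- **Most exposure data need not be missing.** That holds only with incomplete overlap. With full overlap exactly half is missing, and among infants of seropositive mothers about 42%. Using one recall for both purposes is as consistent with the text as using two separate groups.
- **Wider sampling may be planned elsewhere.** Figures 1 and 2, the visit schedule (Appendix 8), the laboratory methods (Appendix 10) and the follow-up data list (Appendix 12) are not in the text available to me. They could show milk taken from every control mother, so absence from the plan as a whole cannot be claimed.
- **A same-dyad rule is not free.** Objective 1 sizes serology at 200 mothers, and nothing says every control infant's mother is tested. Some may need serology on stored blood before being chosen.
- **The objective is exploratory.** The listed Objective 6 analysis is incidence, which uses all control infants and is unaffected. No power target is set for the shedding question.

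These points narrow the finding to milk and recall swabs and keep it minor. They do not remove it: the stated rules cap coverage for those samples and leave the overlap to chance.

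**Conclusion.** The point holds for breast milk and recall vaginal swabs. As the text stands, at most 42 of 84 control infants (50%, or about 58% of the roughly 72 with seropositive mothers) can have a maternal value from these samples, and the rules permit almost none. For vaginal fluid, the parent-study swabs may fill the gap, but the plan does not commit to quantifying them for these mothers.

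This rests on the expected 42 cases arising, on the plan's 86% seropositivity, and on the unseen figures and appendices not specifying wider sampling. It affects one exploratory risk-factor question. It does not bear on the incidence of postnatal infection or on any primary objective. It is worth settling before enrolment because the change is small and the milk cannot be collected afterwards.

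**What to change.** In the Section 3.3 text after Figure 1 and in the Objective 5 sample-size paragraph, require that each Objective 5 control mother be a seropositive mother of one of that case's two Objective 3/6 control infants. Reconcile the matching factors across those two paragraphs and the Study participants paragraph of Section 3.4, so that one set of criteria serves both purposes. State that CMV will be quantified in the stored parent-study vaginal swabs of all control infants' mothers, and name the shedding comparison in the Objective 6 analysis row.

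The cost is serology on stored blood for control-infant mothers not already tested, PCR on stored swabs for up to 84 mothers, and slightly tighter matching. By step 6 about one case in 42 would have no seropositive control mother at the first draw and would need a replacement rule. The same-dyad rule adds no new milk or recall swabs and aims for 42 linked dyads.

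Taking milk from all 84 control mothers is optional. It would raise planned milk coverage from at most 50% to 100%, at the price of about 84 − 42 = 42 further milk samples and PCRs.

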### **Methods**

This study will be nested within a larger cohort study of 35000 mother infant dyads to investigate a sero-correlate of protection against invasive GBS disease (HREC 140203) currently underway at Chris Hani Baragwanath Academic Hospital (CHBAH) in Soweto. A cross sectional study design screening 2200 mother-newborn pairs enrolled in V98\_28OBTP that consent to this study will be undertaken identifying cases of congenital CMV by saliva PCR. A longitudinal cohort study following up the cases of congenital CMV matched to a CMV negative cohort of newborns will measure the incidence of and risk factors for neurological sequelae until infants are 12 months of age. To measure the association between congenital CMV infection and neonatal death and stillbirths, a longitudinal study on causes of death in under 5 children by Minimally Invasive Tissue Sampling (MITS), which is currently underway (HREC 150215), will include tissue processing for CMV. Maternal CMV seroprevalence will be determined by serological methods as well as the association between vaginal CMV shedding and congenital CMV infection.

These studies will identify CMV seroprevalence in pregnant women which is thought to be high (>70%) and will determine the prevalence of congenital CMV infection in Soweto through universal newborn screening which has only previously been done in symptomatic newborns at CHBAH. This study will also provide the first estimates on the incidence of SNHL and other neurological impairment in CMV infected newborns, adding to the current discussions on increasing resource allocation to universal newborn hearing screening. The measure of the effect of HIV exposure on the prevalence of congenital CMV and the burden of subsequent neurological disability will add to the growing global knowledge on congenital CMV in various settings impacting the prevention, diagnosis and management of infected infants.

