Data on congenital CMV infection among HIV exposed infants in sub-Saharan Africa are limited. A Kenyan study of infants born to mothers on perinatal Zidovudine, identified congenital CMV rates of 29% (4/14) in HIV-infected infants and 2.7% (1/37) in HIV exposed but uninfected infants. Zambian newborns admitted to a referral neonatal unit had a congenital CMV prevalence of 3.8% (15/395) whilst prevalence in HIV exposed newborns was 11.4% (9/79). Although HIV prevalence in South African pregnant women is one of the highest in the world (29.9%), a single study has evaluated the relationship between congenital CMV and HIV exposure. In Cape Town, Manicklal et al (2013) found a congenital CMV prevalence of 2.9% (22) in 748 HIV exposed babies. Maternal CD4+ count <200 cells/µL was independently

associated with congenital CMV. Clinical outcomes in these infants and prevalence of congenital CMV among HIV unexposed newborns were not investigated.

**Perinatal and Postnatal CMV infection:** Perinatal CMV infection is defined as CMV infection after 22 completed weeks (154 days) of gestation and seven completed days after birth. Postnatal CMV acquisition is CMV infection acquired any time after birth through consumption of breast milk from CMV seropositive, lactating mothers is common. Most term infants with perinatal CMV infection are asymptomatic, as maternally transferred CMV IgG antibody provides adequate protection against disease. However, studies have identified a significant risk for low-birth-weight (LBW), premature infants for the development of CMV disease such as pneumonia, hepatitis or sepsis-like illness. Data on severity and incidence of disease and long term impact in these infants is currently lacking requiring further study.

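### The 42 expected CMV cases assume two equal HIV groups with no 10% loss removed, but the available text plans consecutive sampling and does not say how 1:1 is reached

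*Combined protocol and SAP*

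**What the plan says.** Section 3.3 (Sample size, Objective 2) starts from congenital CMV prevalences of 2.9% in HIV-exposed and 1.0% in unexposed neonates and arrives at "a total sample of 1662 neonates with 831 HIV exposed and 831 unexposed (1:1 ratio) for 80% power". It continues: "This will be increased to 2160 neonates, to accommodate objective 3". The group sizes follow: "After adjusting for 10% being non-evaluable, 1077 HIV exposed (providing 31 CMV infected) and 1077 HIV unexposed infants (providing ~11 CMV cases) are required".

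The resulting 42 cases are used twice more. Objective 5 in section 3.3 takes 42 as the expected number of case mothers and adds 42 controls. Section 3.4 requires 42 infected infants and 84 controls (126 in all) for Objective 3, and says this already allows for 10% lost to follow-up.

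The design line of section 3.3 reads "Cross-sectional study design with consecutive sampling". Table 1 selects mothers on parent-study enrolment, age, consent, a live birth and residence ("Residing in Soweto and would be available for study follow-up"). HIV status is not a criterion. The synopsis describes "A cross sectional study design screening 2200 mother-newborn pairs" and says that the work "will determine the prevalence of congenital CMV infection in Soweto through universal newborn screening". The only maternal HIV prevalence given for South Africa is the national 29.9% in section 1.2.

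**The concern.** A 1:1 HIV split will not arise by itself from consecutive enrolment in a population where about 30% of pregnant women have HIV. It needs a rule, such as closing each HIV group when full, and the available text gives none. Without a rule, field staff cannot tell whether to stop at a total or to fill two groups, and the two approaches give different case counts.

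The count matters because 42 is the stated requirement for the Objective 3 cohort and the planning figure for Objective 5. The HIV mix matters too. Table 3 plans tests of maternal ART use and CD4 count among HIV-exposed infants, and those tests depend on how many exposed cases are found.

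A second, smaller matter is the 10%. Section 3.3 says an adjustment for non-evaluable infants has been made, but the yields show no sign of it.

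**Working it through.** **Inputs.** Prevalences 2.9% and 1.0%, group sizes 831 and 1077, total 2160 (section 3.3); 2200 pairs (synopsis); maternal HIV share h = 29.9% (section 1.2, national, so an assumption for Soweto); 42 cases, 84 controls, 17% against 1%, 10% loss (section 3.4). Two further assumptions: two-sided 5% significance, which is not stated beside the calculation but reproduces the 831, and a range of 25-40% for h.

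**The plan's own figures.** The pooled normal formula for two proportions, 80% power and no continuity correction, is n = [1.96 x sqrt(2 x 0.0195 x 0.9805) + 0.8416 x sqrt(0.029 x 0.971 + 0.010 x 0.990)]^2 / 0.019^2. It gives 831 per group, as stated. The yields also reproduce:
- exposed: 1077 x 0.029 = 31.2
- unexposed: 1077 x 0.010 = 10.8
- total: 42.0

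**Simple consecutive sampling.** Expected cases = N x [h x 0.029 + (1 - h) x 0.010].

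| h | Overall prevalence | Cases, N = 2160 | Cases, N = 2200 | After one 10% loss |
|---|---|---|---|---|
| 25% | 1.475% | 31.9 | 32.4 | 28.7-29.2 |
| 29.9% | 1.568% | 33.9 | 34.5 | 30.5-31.0 |
| 40% | 1.760% | 38.0 | 38.7 | 34.2-34.8 |

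At 29.9% and N = 2160 there are 646 exposed infants (646 x 0.029 = 18.7 cases) and 1514 unexposed (1514 x 0.010 = 15.1 cases). No share in the range reaches 42.

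**The 10%.** The stated yields are the full 1077 times prevalence. Also, 2 x 1077 = 2154, essentially the 2160 quoted before the adjustment; inflating 2160 for a 10% loss would give 2160/0.9 = 2400. Two readings are possible:
- 42/0.039 = 1077 and 38/0.9 = 42.2. So the 10% may be the Objective 3 follow-up loss, already inside the 42. Then only the wording in section 3.3 is wrong.
- If it is a separate screening loss, it was not applied. The 1:1 yield is then 1077 x 0.9 x (0.029 + 0.010) = 28.1 + 9.7 = 37.8.

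**Power, Objective 2.** By the same z method, 646 against 1514 gives 0.857, or about 0.82 after a 10% loss.

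**Power, Objective 3.** Power = Phi{[0.16 - 1.96 x sqrt(p(1 - p)(1/n1 + 1/n2))] / sqrt(0.17 x 0.83/n1 + 0.01 x 0.99/n2)}, where p is the pooled proportion.
- 34 cases and 68 controls: p = (5.78 + 0.68)/102 = 0.0633; (0.16 - 0.1003)/0.0655 = 0.91; power 0.82.
- As planned, 38/76 after loss: 0.853.
- 30-31 cases after loss, controls at 1:2: 0.777-0.788.
- 30-31 cases with 76 evaluable controls kept: 0.819-0.824.
- Over 29-35 evaluable cases: 0.77-0.83 at 1:2, and 0.81-0.84 with 76 controls.
- Two-sided Fisher: 0.90 at 38/76, 0.816 at 30/60, 0.830 at 31/62, 0.802 at 30/76, 0.821 at 31/76.

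**Overall prevalence if 1:1 is enforced.** Pooled without weights, 42/2154 = 1.95%, against 1.57% at 29.9% HIV. The ratio is 1.24 (1.32 at 25%, 1.11 at 40%).

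**The case against.** The best reply is that section 3.3 sets a requirement for each HIV group, and that each group can be filled consecutively. An eligibility table need not carry a quota. Maternal HIV status is collected (Table 2), and the parent cohort is much larger than this study needs. A rule may also sit in Figure 1 or in Appendices 2, 3 or 9, which were not available. This reply stands. A reader might infer that the documents contradict themselves, or that the study is bound to miss its case count. They do not show that. They show an unstated mechanism and a yield that is wrong if sampling is simply consecutive.

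A reader might also infer that the planned prevalence estimate is biased upward by about 24%. The analysis plan does not support that. Table 3 reports prevalence separately for exposed and unexposed infants, and section 3.5 uses the Objective 2 prevalence by HIV-exposure status. A 1:1 sample leaves those estimates unaffected. The 24% would apply only to an unweighted overall figure, which the synopsis suggests but no listed analysis produces.

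Nor is Objective 3 shown to be seriously underpowered. By the z method, 33 evaluable cases at 1:2 are enough for 80%, so 42 carries some slack. The fall in HIV-exposed cases from 31 to about 19 is real under simple consecutive sampling, but the ART and CD4 tests have no stated size target. Finally, 2154, 2160 and 2200 differ by about 2% and may be rounding.

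**Conclusion.** The point holds in a limited form and is minor. The 42 cases require equal HIV groups of 1077 with nothing removed for loss, and the available text does not say how equal groups are obtained. Under simple consecutive sampling the expected yield is about 34, with about 19 HIV-exposed. This rests on the protocol's own two CMV prevalences and a national HIV figure applied to Soweto; the 32 to 39 range rests on an assumed 25-40% HIV share.

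The consequence for power is small: above the planned 80% for Objective 2, and roughly 78-82% for Objective 3 at 29.9% HIV after a 10% loss, depending on how many controls are kept. The 10% in section 3.3 is either mislabelled, which costs nothing, or was not applied, in which case even a 1:1 sample yields about 38. The documents do not settle which.

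**What to change.** Choose one sampling mechanism and state it in the design line of section 3.3.

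- **Option A.** State that mothers are enrolled consecutively within two HIV groups, each closed at 1077, and that any overall Soweto prevalence is weighted by HIV status. The HIV-specific prevalences in Table 3 and section 3.5 need no change. The cost is recruitment effort: 1077/0.299 = about 3600 eligible, consenting mothers to go through (about 2700 at 40% HIV, 4300 at 25%). That is about 24% (18-29%) of the 15 000 parent-study enrolments outstanding at November 2015 (35 000 - 20 000). The fraction would be larger if fewer remain when this study starts.
- **Option B.** Keep simple consecutive sampling and restate the yield as about 34 cases (30-31 after a 10% loss). Bring the Objective 3 and 5 sizes and power into line, and say whether the 84 controls are kept (about 82% power) or shrink with the cases at 1:2 (78-79%). This needs no extra recruitment.

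Under either option:
- Define the 10% once. If it is the follow-up loss already in the 42, remove the non-evaluable clause from section 3.3. If it is a separate screening loss, restate the 1:1 yield as about 38.
- Use one screening total in place of 2154, 2160 and 2200.

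If Figure 1 or an appendix already contains a quota rule, repeating it in section 3.3 settles the sampling part.
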